#### **9.2.1. Summaries of Adverse Event Incidence Rates for All Subjects**

The primary presentation of AEs data is prepared without regard to causality or relationship to study medication and classifies events using the most recently available MedDRA dictionary with respect to preferred term and body/organ system for all treated subjects by cohort and overall. Subjects will be counted only once at the body system level and will be counted once for each applicable preferred term; multiple occurrences of the same preferred term for a subject will be counted only once. Subjects who experience more than one event within the same body system are counted once at each preferred term level.

Supplementary tables summarize the events with respect to the maximum severity observed for each preferred term and highest relationship to study medication by cohort and overall. The presentation of adverse events with respect to the severity or intensity of the event usually categorizes the data as mild, moderate, or severe.

The relationship of the event to study medication will be collapsed into two categories, related and not related:

1. Related combines the options possible, probable, and highly probable.
2. Not related is a combination of unlikely and not related.

A by-subject listing of serious adverse event data will be presented.

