- Baseline Assessment Visit at the PI's clinic, including electronic completion of ClinRO measures by the PI/certified HCP designee and PRO measures by the patient (by use of a smartphone, tablet, or desktop, based on site and patient electronic capabilities) (Study Day 1)
- Telephone follow-up with the patient by the PI/certified HCP designee (Study Day 30)
- Primary Endpoint Assessment Study Visit at the PI's clinic including electronic completion of ClinROs by the PI/ certified HCP designee and PROs by the patient (Study Day 60)

Eligible patients who compliantly complete the Main Study may participate in the 4-month Extension Study ([Table 3:Schedule of Assessments](#)), which will include:

- Two follow-up Study Visits at the PI's clinic, including electronic completion of ClinROs by the PI/certified HCP designee and PROs by the patient (Study Days 90 and 180)
- One scheduled PRO assessment to be completed electronically by the patient on Study Day 120

If an enrolled patient discontinues XADAGO treatment for any reason at any point in the study (i.e., prior to Study Day 60 for the Main Study or Study Day 180 for the Extension Study), the patient is permitted to remain on study and complete the full schedule of assessments per protocol, as long as the patient is otherwise eligible and is able and willing to continue participation and complete the Main Study (through Study Day 60) or the Extension Study (through Study Day 180).

Number of Patients (planned):

Up to 540 patients enrolled

Inclusion Criteria:

1. Patient (and Care Partner, if required per Inclusion Criterion 7) is able to understand and provide signed informed consent and HIPAA authorization in English
2. Patient with diagnosis of idiopathic PD (all stages)
3. Male or female, 30 to 80 years of age, inclusive, at initial screening assessment
4. Independent of the study, clinician's and patient's choice of treatment is XADAGO in accordance with the Package Insert indication ([Appendix A](#))
5. Patient is willing and able to participate in the study and complete study-related assessments for 2 months and, if eligible, continue for a 4-month study extension
6. Patient has access to an electronic device for the interim completion of PROs

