7. Patient has an available Care Partner who is able and willing to assist with clinic attendance and completion of study assessments (e.g., PROs, health outcomes, etc.), if in the PI's opinion, assistance is needed to comply with all study visits and procedures

Exclusion Criteria:

1. Any of the warnings, precautions, or contraindications listed in the Package Insert ([Appendix A](#)) that in the opinion of the PI would prevent appropriate treatment with XADAGO or impair study participation (e.g., pregnancy, lactation, severe hepatic impairment, etc.)
2. Participation in any other clinical trial of an investigational drug or device within 4 weeks prior to the Baseline Visit or at any time during the study
3. Patient is currently receiving chemotherapy or radiation for any form of cancer (if history of cancer, must be in clinical remission at study entry) or currently receiving immunotherapy
4. Patients with conditions that are likely to prevent them from accurately and reliably completing study assessments, including evidence of moderate or severe dementia as determined by the clinician (not to include mild cognitive impairment [MCI]); major psychiatric illness (specifically diagnosis of schizophrenia, bipolar disorder or a history of attempted suicide); and/or severe and progressive medical illness (including terminal cancer, end-stage renal disease +/- undergoing dialysis)
5. Severe or unpredictable dyskinesia at the time of the Baseline Visit
6. Previous participation in this study; a patient may not re-enroll after prior discontinuation or completion

Medicinal Product, Dosage and Mode of Administration:

XADAGO (safinamide) tablets, 50 mg and 100 mg, oral.

Duration of Patient Participation:

Planned patient participation will be 2 months for patients in the Main Study, including Baseline Assessment and Primary Endpoint Visits at the PI's clinic, and a telephone Follow-up Visit. A window of ± 7 days is allowed for the Baseline Assessment Visit.

Eligible patients participating in the Extension Study (if applicable) will be in the study for a total of 6 months. A window of ± 14 days is allowed for the Clinic Visit on Study Day 180.

Criteria for Evaluation:

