11.4. Recording Adverse Events

AEs spontaneously reported by the patient and/or in response to an open question from the study personnel or revealed by observation will be recorded during the study at the investigational site.

Information about AEs (and SAEs) will be collected from the time the patient signs the informed consent for this study and takes the first study dose of XADAGO until the patient’s last follow-up visit. The AE term should be reported in standard medical terminology when possible. For each AE, the investigator will evaluate and report the onset date, resolution date, intensity, causality, action taken, serious outcome (if applicable), and whether or not it caused the patient to discontinue the study.

Intensity will be assessed according to the following scale:

- Mild (awareness of sign or symptom, but easily tolerated)
- Moderate (discomfort sufficient to cause interference with normal activities)
- Severe (incapacitating, with inability to perform normal activities)

It is important to distinguish between serious and severe AEs. Severity is a measure of intensity whereas seriousness is defined by the criteria under Section 11.2.2. An AE of severe intensity may not be considered serious.

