## **6.4. Data Presentation Conventions**

Continuous variables (e.g. age) are summarized using descriptive statistics (the number of subjects with available data, the mean, standard deviation (SD), median and minimum and maximum). Categorical variables (e.g. race) are summarized using counts and percentages. Percentages are calculated using the total subjects in the XADAGO group.

The following conventions are applied to all data presentations and summaries.

- For continuous variables, all mean and median values are formatted to one more decimal place than the measured value. Standard deviation values are formatted to two more decimal places than the measured value. Minimum and maximum values are presented with the same number of decimal places as the measured value.
- For categorical variables, the number and percentage of responses are presented in the form XX (XX.X%) where the percentage is in the parentheses.
- Date variables are formatted as DDMMYY for presentation. Time is formatted in military time as HH:MM for presentation.
- Wherever possible, data will be decimal aligned.
- Unless otherwise stated, any statistical tests performed will use 2-sided tests at the 5% significance level.

The table and listing shells and table of contents as part of this SAP provide the expected layout and titles of the tables, listings and figures. Any changes to format, layout, titles, numbering, or any other minor deviation will not necessitate a revision to the SAP nor will it be considered a deviation from planned analyses. Only true differences in the analysis methods or data handling will necessitate such documentation. The appropriate listings supporting the tables will be included and are not specified in the individual sections throughout the document.

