### **9.1. Overall Summary of Tolerability**

The overall summary of tolerability table presents the data for all treated subjects by cohort and overall. Entries in this table are the number of:

1. Subjects treated and subject months of drug exposure by treatment (50 mg vs 100 mg).
2. Subjects with adverse events.
3. Adverse events.
4. Subjects with serious adverse events.
5. Subjects discontinuing due to adverse events.
6. Deaths.

The subject data listing provides a complete disclosure of adverse events as recorded in the CRF and supports this table and all other AE summary table subsets.

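### Adverse event percentages pool about 2 and about 6 months of follow-up with no Day 60 cut and no exposure adjustment, so they depend on Extension uptake

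*SAP*

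**What the plan says.** Follow-up differs by design. The Protocol synopsis states "Planned patient participation will be 2 months for patients in the Main Study" and "Eligible patients participating in the Extension Study (if applicable) will be in the study for a total of 6 months". The Extension is optional and selective: "Eligible patients who compliantly complete the Main Study may participate in the 4-month Extension Study". Expected uptake is not given, overall or by cohort.

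Under Protocol 11.4, AE collection starts when the patient has consented and "takes the first study dose of XADAGO until the patient’s last follow-up visit". AE assessments are scheduled at Days 60, 90 and 180.

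SAP 9.2 restricts the tables to treatment-emergent events, counted up to 2 days after stopping treatment if non-serious and up to 30 days if serious. Within that window SAP 9.2.1 applies a per-patient rule: "Subjects will be counted only once at the body system level and will be counted once for each applicable preferred term", and "multiple occurrences of the same preferred term for a subject will be counted only once". The tables cover all treated patients, by cohort and overall. The general rule in SAP 6.4 gives a head-count denominator: "Percentages are calculated using the total subjects in the XADAGO group". SAP 9.2.3 summarises serious AEs, AE dropouts and deaths with no stated period.

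SAP 9.1 places subject-months of drug exposure, by dose, in the same table as the AE counts, by cohort and overall. SAP 7.1 reports disposition at both Day 60 and Day 180. No section does the same for AEs, and none plans an exposure-adjusted rate.

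**The concern.** The tables are headed as incidence rates, but each figure is a proportion of patients with at least one event over unequal observation. A patient followed for 6 months has three times the planned opportunity to contribute an event as one followed for 2 months (Day 180 / Day 60 = 3). The overall percentage is therefore a mixture whose weights are set by how many patients enter the Extension, which has nothing to do with the drug's risk.

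Two uses are affected. The overall percentage cannot be quoted as a risk over any defined period or set beside a figure that has one. The cohort columns can also differ when the underlying AE risk does not, if one cohort supplies more Extension patients or stays on treatment longer.

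**Working it through.** The documents state no AE rate, AE precision or AE-based sample size, so there is no planned figure to reproduce. What follows is an illustration.

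**Inputs from the documents:** follow-up of 2 months (Main only) and 6 months (Extension); one count per patient; patients as denominator.

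**Assumed inputs:** 2-month risk *p* of 5% to 30%, identical in every cohort; Extension uptake *u*, which may differ by cohort; hazard after month 2 equal to *f* times the earlier hazard; full planned follow-up on treatment; the same risk in those who do and do not enter the Extension.

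**Formulas**
- 6-month risk = 1 − (1 − p)^(1 + 2f), which is 1 − (1 − p)³ for a constant hazard (f = 1).
- Expected crude percentage = (1 − u) × p + u × (6-month risk).

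**Step 1, one case in full.** With p = 10% and f = 1, the 6-month risk is 1 − 0.9³ = 27.1%. At 30% uptake the table shows 0.7 × 10% + 0.3 × 27.1% = 15.1%. At 70% uptake it shows 0.3 × 10% + 0.7 × 27.1% = 22.0%.

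**Step 2, range of risks, constant hazard, uptake 30% against 70%** (differences and ratios from unrounded values)

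| 2-month risk | 6-month risk | 30% uptake | 70% uptake | Difference (points) | Ratio |
|---|---|---|---|---|---|
| 5% | 14.3% | 7.8% | 11.5% | 3.7 | 1.48 |
| 10% | 27.1% | 15.1% | 22.0% | 6.8 | 1.45 |
| 20% | 48.8% | 28.6% | 40.2% | 11.5 | 1.40 |
| 30% | 65.7% | 40.7% | 55.0% | 14.3 | 1.35 |

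**Step 3, the overall figure alone.** With p = 20% and 50% uptake, the table shows 0.5 × 20% + 0.5 × 48.8% = 34.4%, which is neither the 2-month nor the 6-month risk. No cohort comparison is involved.

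**Step 4, sensitivity of the cohort ratio** (true ratio 1.00; ranges are over p of 5% to 30%)
- Other uptake contrasts, constant hazard: equal uptake 1.00; 40% against 60%, 1.16 to 1.21; 20% against 80%, 1.58 to 1.81.
- Uptake 30% against 70% with a lower hazard after month 2: halved, 1.23 to 1.30; a quarter, 1.14 to 1.17; zero, 1.00.

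**Step 5, the same case after the fix.** With p = 10% and constant hazard, the monthly hazard is −ln(0.9)/2 = 0.0527. Both cohorts then show 10.0% by Day 60 and 5.27 first events per 100 subject-months, whatever their uptake.

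**The case against.** Counting each patient once is a conventional display. Safety is not the principal objective (Protocol 11.1), Protocol 12.9.2 asks only that AEs be reported by cohort and overall, and no formal comparison of AEs between cohorts is planned. Three stronger readings are tempting, and the documents support none of them.

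- A reader might infer that AEs are counted over each patient's whole participation. They are not. SAP 9.2 closes the count 2 days (non-serious) or 30 days (serious) after treatment stops, and patients may remain on study off drug (Protocol 10.1.4). The count can therefore end well before participation does. Patients who stay on treatment are still observed for about 2 or about 6 months, so the imbalance remains.
- A reader might infer that the safety output has no time base at all. SAP 9.1 shows subject-months beside the AE counts by cohort, so one crude overall rate per cohort could be worked out by hand. What is missing is a planned rate, and any time base for the preferred-term and body-system tables.
- A reader might infer that the cohorts cannot be compared. That is conditional: uptake or duration must differ by cohort, and AEs must keep accruing after Day 60. The documents settle neither.

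Two further cautions stand. The 30% against 70% contrast is chosen for illustration, and because Extension entrants must have completed the Main Study compliantly, their risk may not equal that of other patients. The full 6 months is also not secure in the final output: SAP 5.2 locks the database after the last patient's Visit 3 and describes no later lock, and SAP 9.2 does not say which visit ends AE capture.

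**Conclusion.** The point holds in a limited form. The planned AE percentages in SAP 9.2.1 and 9.2.3 are crude, pool about 2 and about 6 months of planned follow-up, and correspond to no defined risk period. That follows from the counting rule and the design whenever some but not all patients enter the Extension and events occur after Day 60.

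The effect on cohort contrasts is possible but not established. With equal true risk and uptake of 30% against 70%, the ratio of crude percentages is 1.35 to 1.48 under a constant hazard and 1.23 to 1.30 if the later hazard is halved. It is 1.00 if uptake is equal or nothing occurs after month 2. These values rest wholly on assumed hazards and uptakes. This is an inexpensive improvement to a descriptive safety output, and it does not affect the main outcome analysis.

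**What to change.** Amend SAP 9.2.1 and 9.2.3 as follows.

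1. Make the main AE and serious AE tables those with onset from first dose to Visit 3, or to Day 60 for a patient with no Visit 3, with all treated patients as denominator.
2. Tabulate later-onset events separately, with Extension entrants as denominator.
3. Add first events per 100 subject-months by cohort. Match person-time to the SAP 9.2 counting windows (2 days after stopping for non-serious events, 30 days for serious events). The drug exposure in SAP 9.1 is not the right denominator on its own, because serious events can be counted after exposure has ended.
4. State the data cut-off for Extension AEs, given the lock in SAP 5.2, and name the visit that SAP 9.2 means by the follow-up visit.

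Onset dates are already recorded under Protocol 11.4 and exposure is already derived for SAP 9.1, so no new data are needed. The cost is SAP wording, programming of the person-time, and a few more tables.

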### **9.2.2. Missing and Partial AE Onset Dates**

The start dates for AEs are important for the:

1. Treatment emergent algorithm.
2. Designation of unique AE occurrences.

Completely missing or partially missing AE onset dates will be imputed. The imputation rule is described in Section [6.8.1](#).

Imputed dates will be flagged in the individual supportive subject listings.

### **9.2.3. Summaries of Adverse Incidence Rates for Serious Adverse Events (SAE), Adverse Event Dropouts, and Death**

Adverse event incidence rates, by body system, will be summarized for subjects who report a non-fatal serious adverse event, discontinue treatment prematurely due to an adverse event, and deaths.

A by-subject listing of premature discontinuations due to all causality will be presented.

## **9.3. Study Termination Status**

This post text table categorizes the status of the subjects at the end of the study. The completion status is summarized with respect to the number of subjects by cohort and overall:

1. Completing the entire course of treatment.
2. Discontinuing the trial prematurely.
3. Reason for premature study termination.

The reasons for early study termination are adverse event, protocol violation, screen failure, administrative, lack of efficacy, lost to follow-up, death, other, etc.
